Bronchopulmonary dysplasia remains a leading morbidity of the extremely preterm infant, resistant to therapeutic interventions and associated with adverse neurodevelopmental outcomes (1-3). Most studies indicate that its rate of occurrence has not decreased in recent years (4), and several reports suggest that the incidence and/or severity of the disease may be increasing as postnatal glucocorticoid use has decreased (5-7). Although dexamethasone can facilitate extubation and decrease the incidence of BPD (8, 9), such treatment can be associated with increased risk of short- and long-term complications including impaired growth and neurodevelopmental delay (10 – 12). However, because BPD also is associated with increased risk for death and adverse neurodevelopmental outcomes, meta-analyses have suggested that in populations at high risk for death or BPD even dexamethasone therapy may be associated with net benefit (9, 13). Lower doses of dexamethasone may have equal pulmonary benefit with less toxicity (14 – 17); however, because it has a very long biologic half-life, suppresses endogenous cortisol production and disrupts the balance between mineralocorticoid and glucocorticoid in the brain (see below), dexamethasone may still be an inferior glucocorticoid choice for premature infants. Establishment of an alternative therapeutic agent to facilitate extubation may improve respiratory outcomes for these extremely preterm infants at very high risk for BPD, without the adverse effects previously seen with dexamethasone therapy.

HYPOTHESIS

Compared to placebo, hydrocortisone treatment of infants <30 weeks estimated gestational age at birth who remain on mechanical ventilation at 14 – 28 days postnatal age will significantly improve their rate of survival without moderate or severe BPD and will be associated with improvement in survival without moderate or severe neurodevelopmental impairment at 22 - 26months corrected age.

SPECIFIC AIMS

- To determine whether a 10 day course of hydrocortisone results in a significant increase in survival without moderate or severe BPD;
- To determine whether a 10 day course of hydrocortisone results in a significant increase in the number of infants successfully extubated during treatment;
- To determine whether this treatment affects other short-term outcomes including respiratory morbidities, growth and length of stay;

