We will include infants who have failed extubation because of apnea, because they too are at risk for BPD from prolonged intubation. HC may promote successful extubation in these infants by decreasing ongoing lung inflammation and capillary leak and improving FRC.

(3) Exclusions:

- (a) Major congenital anomalies
- (b) Decision to limit support
- (c) Indomethacin or ibuprofen treatment within 48 hours of study drug
- (d) Previous corticosteroid treatment for BPD
- (e) Hydrocortisone treatment for hypotension in the first week of life is common (35) and will not be an exclusion; however, infants will be excluded if they have received hydrocortisone or any other systemic glucocorticoid:
 - (i) for ≥ 14 cumulative days OR
 - (ii) within 7 days of study entry.
- (f) Enrolled in a conflicting clinical trial

(4) Study procedures

(a) Ascertainment of study eligibility: Prior to the 14th postnatal day, the clinical care team will be asked whether they plan to extubate a potentially eligible infant within the next 24 – 48 hours. If so, approach for parental consent will be deferred for that time period. If the infant is not extubated by the 14th postnatal day, or if he/she fails extubation within the study window, AND if the attending physician agrees to the patient's entry into the study, then the parents will be approached for consent.

(b) Randomization procedures:

- i. Infants will be randomized 1:1 to the two arms using a stratified, permuted block design with strata for gestational age as described above within center.

- ii. After parental consent is obtained, the NRN coordinator at each center will randomize subjects by telephoning the Data Coordinating Center at RTI International, Research Triangle Park, NC; the randomization system will be available 24 hours per day, 7 days per week.
- iii. Pharmacy personnel will prepare and dispense study drug in accordance with procedures described in the study manual. HC and normal saline placebo are indistinguishable in appearance.

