(a) Respiratory support: Each center currently cares for these infants with techniques they feel appropriate, whether CPAP, CPAP with IMV, high-flow nasal cannula or other. This study will not prescribe the technique to be used. Because this is an RCT and because enrollment will be stratified by center and study treatment will be masked, the center-specific and attending-specific techniques should be balanced in both treatment groups equally over the course of the trial and therefore not introduce bias.

(b) Open-label glucocorticoid therapy

(i) Infants who remain successfully extubated are not to be treated with open-label glucocorticoids as therapy for BPD. This will be a protocol violation.

(ii) Infants who are not extubated during the study treatment period or who are subsequently re-intubated may be treated with open-label dexamethasone after ≥ 4 days following the last dose of study drug. Open-label dexamethasone will be encouraged to be prescribed as described by Doyle (15). Further treatment with HC for prevention/treatment of BPD will be considered a protocol violation. The rationale for this plan is as follows: (1) HC has not been demonstrated in an RCT to be efficacious for extubation, whereas dexamethasone has (8, 9, 15); (2) this design will permit a true RCT of HC without open-label contamination of the placebo group. At the same time, we will not be denying treatment to the group of infants that meta-analysis suggests derive net benefit from treatment with dexamethasone (13)

(6) Definition of successful extubation: An infant who remains extubated for at least one week, including at least 3 days (72 hours) after the last dose of study medication, will be considered to be successfully extubated in response to this treatment.

(7) Laboratory specimens: none

(8) Analysis of study outcomes

(a) Study specifications and definitions

(i). Analysis will be by intention to treat.

(ii) Moderate or severe BPD is defined as the need for supplemental oxygen by NRN physiologic definition at 36 weeks estimated gestational age. This includes an oxygen withdrawal test for infants receiving $<0.30\text{FiO}_2$, as described in the study manual of procedures. For this study, this determination will be made between 36⁰ to 36⁶ weeks.

(iii) Infants discharged on oxygen prior to 36 weeks gestation will be evaluated at 36 weeks gestational age at a follow-up clinic visit, a home visit or by telephone if necessary.

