This study will provide a sequential evaluation of the composite hypothesis that (i) administration of hydrocortisone has efficacy benefit in that it reduces the risk of death or BPD at 36 weeks; and (ii) administration of hydrocortisone has an acceptable long-term safety profile with respect to death or NDI at 22-26 months. Specifically, the primary outcome for this study will include both a measure of efficacy (improvement in survival without BPD) and safety (survival without major NDI at 22 - 26 months corrected age). This composite hypothesis will be evaluated sequentially. First, point and interval estimates of the adjusted relative risk obtained from a robust Poisson regression model controlling for center and gestational age will be used to test the hypothesis that infants treated with hydrocortisone had a lower risk of death or BPD at 36 weeks than infants treated with placebo. If this test of efficacy indicates benefit of the hydrocortisone arm then the safety of the treatment will be evaluated descriptively through an assessment of the risk to benefit ratio of the hydrocortisone treatment. Specifically, this safety outcome will be considered a “success” if either (1) the point estimate of risk of death/NDI is lower on the hydrocortisone arm than on the control arm, or (2) there is an increase in risk on the hydrocortisone arm, but the lower limit of a one-sided 95% confidence interval for the ratio of increased benefit for BPD to increased risk for NDI is greater than 4. In other words, for every additional 4 infants surviving without BPD, no more than 1 additional infant would experience death/NDI.

(c) Power calculations and sample size:

Consistent with the approach for evaluating the composite hypothesis defined above, the sample size calculations were conducted in two stages. First, standard power

analysis software was used to assess the sample size required to demonstrate a difference in death or BPD at 36 weeks on the two treatment arms. Second, simulation analyses were used to assess the probability of success for the safety outcome based on either of the two criteria defined above. The empirical probability of success for the descriptive analyses used to evaluate the safety outcome is analogous to the power of a formal hypothesis test.

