The results indicate that if the improvement in the death or NDI outcome is only 1% on the hydrocortisone arm, then the probability of achieving a “success” on the safety outcome is 0.68 to 0.71 if success requires the lower limit of a 95% confidence interval on the risk benefit ratio to exceed 4, but 0.80 to 0.81 if we only require that the point estimate achieve 4. However, if the true benefit of the hydrocortisone treatment on death or NDI is at least 3% then the probability of achieving a “success” on the safety outcome is 0.83 to 0.86 if success requires the lower limit of a 95% confidence interval on the risk benefit ratio to exceed 4, and 0.90 to 0.93 if we only require that the point estimate achieve 4.

(d) Secondary outcomes and analysis: After analysis of unadjusted risk differences, other factors known to affect neurodevelopmental outcomes (such as gender, maternal education and dexamethasone exposure) will be entered into a multivariable analysis of outcome using the robust Poisson regression models described for the primary efficacy outcome for each of the binary secondary outcomes defined below. Secondary outcomes will include:

(i) Standard NRN measures of morbidity and growth as collected for the GDB at 36 weeks postmenstrual age and at 22 - 26 months corrected age. We will include ROP incidence and severity as a secondary outcome of specific interest, as there has been conflicting information regarding the relationship of dexamethasone to

ROP. We will also include a questionnaire to assess breathing outcomes at 22 - 26 months of age using forms developed for the SUPPORT study.

(ii) Successful extubation during the intervention period.

(iii) Use of open-label dexamethasone

(iii) Respiratory status at 40 weeks estimated gestational age. Assessment of respiratory outcomes at this age has been reported to more accurately predict long term respiratory outcomes (personal communication [name]). This assessment will not include a room air challenge, as repeating the physiologic testing would be burdensome and the 40 week status is not the primary study outcome.

(e) Concomitant medications will be recorded, in particular diuretics, bronchodilators, antibiotics, iNO, caffeine and Vitamin A.

(f) Safety monitoring:

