(1) Futility: hydrocortisone may not prove effective for extubation or reduction of BPD. When approximately 50% and 75% of patients have been evaluated for the survival without BPD efficacy outcome at 36 weeks postmenstrual age, RTI will provide the DSMC with the information required to evaluate whether to stop the trial for futility. The analyses will include formal computation of conditional power for the primary outcome based on the observed data and the effect size and nuisance parameters used for the original study design and for key secondary parameters (including successful extubation during study drug administration, respiratory status at 40 weeks EGA, days on mechanical ventilation, days on positive pressure, days on oxygen, days exposed to open-label dexamethasone or other steroids (including inhaled steroids), length of stay, medications at discharge, growth parameters at 36 weeks EGA, nosocomial sepsis after study entry, necrotizing enterocolitis after study entry and retinopathy of prematurity) based on observed effect sizes and nuisance parameters. Should these analyses show a conditional power for the primary outcome of 0.1 or less and provide the DSMC with little evidence of a benefit for any of the secondary parameters, the DSMC will consider stopping enrollment in the trial for futility. Details for these futility analyses will be included in the DSMC monitoring plan. Patients who have been enrolled in the study will be followed through the 22 - 26month evaluation.

(2) Slow patient enrollment: A timeline for enrollment is proposed, above, based on eligible patients anticipated at the NRN centers. This will be monitored, and if patient enrollment does not meet expected, the reasons for the problem will be analyzed and the potential for study completion assessed. Study forms will be constructed to include reasons for lack of enrollment, to assist in this process.

BUDGET (not including RTI costs) based on 800 patients

Pharmacy cost (avg): \$2000/center set-up fee + \$500/year x 3 years =	\$ 56,000
Per patient (28 doses x \$20/dose) =	\$448,000*
Coordinator time: 10 hours/patient @ \$35/hr (\$350/pt)	\$280,000
Follow up (est. deaths 15%, follow up rate 90% = 612):	
\$400 GDB babies, \$700/pt otherwise (est.2/3)	\$367,200
Estimated total:	\$1,151,200

(*This may be lower, since all doses for each day can be prepared and dispensed at one time)

REFERENCES

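### The adjusted secondary-outcome models include dexamethasone exposure, an essentially post-randomisation variable, so they may not estimate the total effect of assignment

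*Combined protocol and SAP*

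**What the plan says.** Section (8)(d), on secondary outcomes, starts with unadjusted risk differences. It then says that "other factors known to affect neurodevelopmental outcomes (such as gender, maternal education and dexamethasone exposure) will be entered into a multivariable analysis", using the robust Poisson models of the primary efficacy analysis, for every binary secondary outcome. No time window is given for dexamethasone exposure.

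Other parts of the protocol bear on this:

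- **(3) Exclusions, (d):** "Previous corticosteroid treatment for BPD" is an exclusion. Item (e) also excludes other systemic glucocorticoids given for 14 or more cumulative days or within 7 days of entry.
- **(5)(b)(ii), open-label therapy:** "Infants who are not extubated during the study treatment period or who are subsequently re-intubated may be treated with open-label dexamethasone", starting no earlier than 4 days after the last study dose. Under (5)(b)(i), open-label glucocorticoid for BPD in an infant who stays extubated is a protocol violation.
- **Specific Aims:** one aim is "To determine whether a 10 day course of hydrocortisone results in a significant increase in the number of infants successfully extubated during treatment".
- **(8)(d), list of secondary outcomes:** "Use of open-label dexamethasone" is one of them.
- **Possible problems, (1) Futility:** days of exposure to open-label dexamethasone is among the parameters that the DSMC reviews for evidence of benefit.
- **(8)(a)(i):** analysis is by intention to treat.
- **(8)(b):** the primary efficacy analysis uses a "robust Poisson regression model controlling for center and gestational age". Dexamethasone is not in it.

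**The concern.** Sex and maternal education are fixed at randomisation. Dexamethasone exposure, listed beside them, is not. It follows from extubation status, which the treatment is meant to change, and from how ill the infant is after the study course. It is thus a possible mediator of the hydrocortisone effect and a marker of later severity.

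Adjusting for such a variable does two things if hydrocortisone alters it. It removes any part of the effect that acts through dexamethasone. It also compares infants of different severity at the same dexamethasone status, because a treated infant who still needs dexamethasone is not the counterpart of a placebo infant who needs it. The result is not the total effect of assignment, which is what intention to treat implies.

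The plan does not say whether the unadjusted or the adjusted estimate is to be interpreted, and does not call the adjusted one exploratory. ROP is among the outcomes concerned ("We will include ROP incidence and severity as a secondary outcome of specific interest"), and the reason given there is its disputed relation to dexamethasone.

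**Working it through.** **1. When the covariate is measured.** Exclusion (3)(d) removes infants treated with steroids for BPD before entry. Section (5)(b)(ii) opens dexamethasone only after the study course. Exposure for BPD therefore comes after randomisation. A short non-BPD steroid course ending more than 7 days before entry remains possible under (3)(e), so the covariate is essentially, not wholly, post-randomisation.

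**2. Its place in the causal order.** Assignment is meant to change extubation, and extubation status decides who may receive dexamethasone. For the outcome of successful extubation the order is reversed. Section (6) requires at least 72 hours extubated after the last dose, and dexamethasone is allowed only from 4 days after it. That outcome is largely settled first, and dexamethasone is mostly its consequence.

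**3. Size.** The documents give no dexamethasone use by arm, so there is no plan figure to reproduce. Both illustrations below rest on assumed inputs. The 58% outcome risk is 100% minus the 42% control-arm survival without NDI in (8)(c)(ii).

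*Illustration A: severity as a common cause.* Severity U is standard normal, and arm HC is 0 or 1.

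- logit P(dex) = i1 + g·HC + a·U
- logit P(Y) = i2 + b·U + d·dex + c·HC

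The intercepts give 42.5% placebo use (assumed) and placebo outcome risk of 58%, or 20% as a less common outcome (assumed). Poisson regression on the exact cell probabilities, obtained by numerical integration over U, is fitted with and without dexamethasone. With c = 0 and d = 0 the unadjusted RR is 1.000 throughout.

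| g | a, b | Use on HC | Adjusted RR, 58% | Adjusted RR, 20% |
|---|---|---|---|---|
| 0 | either pair | 42.5% | 1.000 | 1.000 |
| −0.35 | 0.6, 0.5 | 34.8% | 1.008 | 1.017 |
| −0.35 | 1.2, 1.0 | 36.0% | 1.022 | 1.045 |
| −0.7 | 0.6, 0.5 | 27.8% | 1.016 | 1.033 |
| −0.7 | 1.2, 1.0 | 29.9% | 1.042 | 1.091 |

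- The falls in use are 42.5 − 36.0 = 6.5 to 42.5 − 34.8 = 7.7 points, and 42.5 − 29.9 = 12.6 to 42.5 − 27.8 = 14.7 points.
- If hydrocortisone raises use by 7 to 8 points (g = +0.35), the adjusted RR at 58% is 0.991 or 0.978.
- With d from −0.3 to +0.3 and a, b up to 2.0, 1.5, the ratio of adjusted to unadjusted RR at 58% runs from 0.999 to 1.067 for lower use.
- With a true benefit (c = −0.12), an unadjusted RR of 0.952 becomes 0.960 (g = −0.35; a, b = 0.6, 0.5), and 0.958 becomes 1.000 (g = −0.7; a, b = 1.2, 1.0).

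*Illustration B: the extubation rule.* Assume that 70% are not extubated on placebo, that 60% of those and nobody else receive dexamethasone, and that the whole effect of hydrocortisone runs through extubation. Non-extubation multiplies risk by 1.3, dexamethasone by 1.0 or 1.3, and a two-level severity factor by 1.0 or 1.4. Dexamethasone use is 0.60 × non-extubation. In the simplest case (multipliers of 1.0 for dexamethasone and severity), with non-extubation cut to 60%, the total RR is (1 + 0.3 × 0.6)/(1 + 0.3 × 0.7) = 1.18/1.21 = 0.975. The dexamethasone-adjusted RR is 0.984.

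| Non-extubation, HC | Use on HC (placebo 42%) | Total RR | Adjusted RR |
|---|---|---|---|
| 70% | 42% | 1.00 | 1.00 |
| 60% | 36% | 0.96–0.98 | 0.98–0.99 |
| 50% | 30% | 0.92–0.95 | 0.97–0.98 |
| 40% | 24% | 0.88–0.93 | 0.95–0.97 |

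Wherever hydrocortisone improves extubation here, the adjusted estimate is nearer 1 than the total effect.

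**4. Scale.** With 400 per arm, SE(log RR) at 58% is √(2 × 0.42/(400 × 0.58)) = 0.060, and at 20% it is √(2 × 0.80/(400 × 0.20)) = 0.141. The shift log 1.042 = 0.041 is 0.7 SE. The extreme log 1.067 = 0.065 is 1.1 SE. At 20%, log 1.091 = 0.087 is 0.6 SE. The 3-point gain postulated in (8)(c)(ii) takes death or NDI from 58% to 55%, an RR of 0.55/0.58 = 0.95, or 0.053 on the log scale.

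**The case against.** The strongest reply is that the total effect is already estimated. Unadjusted risk differences come first, analysis is by intention to treat, and no decision rule uses the adjusted estimates. That is right, and it limits the point to the second-step models. But being done first does not make the unadjusted result the one to be interpreted, and the plan does not say that it is.

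A second reply is that the adjustment may be deliberate, to separate hydrocortisone from open-label dexamethasone, notably for ROP. The documents do not state this purpose. Simple adjustment would not achieve it cleanly, since sicker infants are the ones who receive dexamethasone. The reply supports keeping such an analysis under an exploratory label, not leaving it as the general adjusted model.

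Third, the numbers are illustrative. The 42.5% placebo use is a single assumed value, the severity slopes are assumed, and illustration A has no extubation step. All of this stands. Illustration B does include the step and also moves toward 1, but its inputs are assumed too. The protocol hypothesises better extubation and does not itself predict a change in dexamethasone use. The rule on who may receive it makes such a change plausible, not certain.

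Finally, the literal wording would also adjust dexamethasone use for itself. That is only a wording defect and adds no weight.

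**Conclusion.** The concern holds and should be corrected. As written, the adjusted models for the binary secondary outcomes condition on a variable that is essentially post-randomisation, depends on extubation, and is treated elsewhere in the protocol as an outcome. That reading needs no numerical assumption.

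The size does. If hydrocortisone does not affect extubation or dexamethasone use, nothing shifts. If it lowers use by 6.5 to 14.7 points, illustration A gives +0.8% to +4.2% in the RR at 58% risk and +1.7% to +9.1% at 20%. The direction reverses if use rises. Nearly all of these shifts are below one standard error, but they are systematic, so a larger sample would not remove them. The larger ones at 58% are close to the effect that the trial postulates.

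The unadjusted risk differences, the primary efficacy model and the safety criterion in (8)(b) are not affected.

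**What to change.** In (8)(d):

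- Remove dexamethasone exposure from the covariate list, and state that only variables fixed before randomisation are entered: center, gestational-age stratum, sex and maternal education.
- If the limited pre-entry steroid exposure permitted by (3)(e) was meant, define it as exposure before randomisation.
- State that the unadjusted and baseline-adjusted estimates are the ones interpreted.
- Keep dexamethasone use by arm as the secondary outcome it already is.
- Label any dexamethasone-adjusted or mediation analysis exploratory, and state its assumptions.

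This is a short wording change. It needs no new data, no change in sample size and nothing from patients, and the dexamethasone-adjusted results can still be reported under their label.

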The DCC will compare the incidence of serious adverse events (nosocomial sepsis, intestinal perforation, respiratory deterioration or pneumonia, or death) between the two treatment arms after every 100th infant reaches status (death, discharge, transfer or 120 days of age). Since 800 infants are to be enrolled in this trial, this will involve 8 interim looks, giving a Pocock boundary of ± 2.555 , with a corresponding significance level of 0.011 (Pocock, 1977). Such reports will be forwarded to the Chair of the DSMC when there is any suggestion of a trend towards a difference between the two treatment arms emerging. They will also be made available to the full DSMC at their scheduled meetings after 50% and 75% of the trial infants have been evaluated for the survival without BPD efficacy outcome at 36 weeks postmenstrual age (see Section on futility monitoring on page 16 below). Serious adverse events to be reported to NICHD within 24 hours include death or intestinal perforation with an assessment as best as possible as to the cause of the perforation (NEC, spontaneous, other).

(9) Available population (based on GDB data, 06-07):

To create a conservative estimate of the population available for this study, we obtained from [name] the number of babies 401 – 1500g birth weight who had received ≥ 14 days on mechanical ventilation during the 1st 28 days in the calendar years 2006 and 2007:

1242 (401 – 1000g), 214 (1001 – 1500g)	total = 1456, or 728/year
- If $\frac{3}{4}$ of those meet eligibility	= 546/year
- Consent rate at 60% (direct benefit study*)	= 328/year
- Total over a 3 year enrollment	= 983
- For a sample size of 800	= 30 months

(*glutamine consent rate was 70%)

Competing studies: The primary outcome for inositol is ROP, rather than BPD. Hydrocortisone treatment has not been shown to have effects on ROP. While inositol may have secondary effects on respiratory morbidities, these studies may be compatible. It appears from NRN conversations with the FDA that subjects may participate in more than one IND trial; therefore, this study would not conflict with probiotics.

RISKS, BENEFITS, POTENTIAL PROBLEMS

Risks:

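### The Pocock boundary of ±2.555 for serious adverse events is the 10-look value; the 8 looks stated give ±2.512 at an assumed overall two-sided 0.05. The practical effect is small.

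*Combined protocol and SAP*

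**What the plan says.** Section (8)(f)(ii), Reporting of adverse events, has the data coordinating center compare the incidence of nosocomial sepsis, intestinal perforation, respiratory deterioration or pneumonia, and death "between the two treatment arms after every 100th infant reaches status". Status means death, discharge, transfer or 120 days of age.

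The number of looks and the boundary come in a single sentence. With 800 infants planned, "this will involve 8 interim looks, giving a Pocock boundary of" ±2.555, then "with a corresponding significance level of 0.011", with a citation of Pocock (1977). No overall alpha is stated for these looks.

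The section names no action to be taken if the boundary is crossed. Reports go to the DSMC Chair "when there is any suggestion of a trend towards a difference between the two treatment arms emerging", and to the full DSMC at its meetings after 50% and 75% of infants have been evaluated for the 36-week efficacy outcome. Death and intestinal perforation are reported to NICHD within 24 hours.

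**The concern.** The sentence presents ±2.555 as a consequence of 8 looks. A Pocock boundary is fixed by three things: the number of equally spaced looks, the overall alpha and the sidedness. The first is given as 8, and the ± sign implies a two-sided comparison. At the usual overall level of 0.05 the third decimal of the stated boundary points to a different number of looks.

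This is the only numerical boundary the protocol gives for serious adverse events. Someone who computes it from the stated design will get one figure, and someone who copies it from the text will use another. With no overall alpha stated, the text does not show whether the count of looks or the boundary is the slip. If 8 looks at 0.05 were meant, the slip makes a harm signal slightly harder to reach.

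**Working it through.** **Inputs.** All are from section (8)(f)(ii) unless noted.

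- Looks: K = 800/100 = 8, equally spaced. The eighth falls on the full sample.
- Stated boundary: ±2.555, constant. Stated nominal level: 0.011.
- Sidedness: two-sided, from the ± sign.
- Overall alpha: not stated; 0.05 two-sided is assumed. Indirect support comes from section (8)(c)(i). With n per arm = [1.960·√(2p̄(1−p̄)) + 0.842·√(p₁(1−p₁) + p₂(1−p₂))]² / (p₂−p₁)², 25% against 35% gives 329 per arm (658 in total), and 35% against 45% gives 376 per arm (752). Both are the protocol's own totals, so the efficacy calculation used two-sided 0.05. This supports the assumption for the safety looks but does not prove it.

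**Step 1: is the stated pair consistent with itself?** 2·[1 − Φ(2.555)] = 0.0106, which rounds to 0.011. It is, so a single misread digit does not explain the mismatch.

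**Step 2: the constant boundary for K looks.** Let S_k be the sum of k independent N(0,1) increments and Z_k = S_k/√k. With f₁(s) = φ(s) on |s| < c,

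f_k(s) = ∫ f_{k−1}(u)·φ(s − u) du over |u| < c√(k−1),

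and the overall error is 1 − ∫ f_K(s) ds over |s| < c√K. Solving for an overall error of 0.05 by numerical integration:

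| Looks K | Boundary | Nominal two-sided p |
|---|---|---|
| 7 | 2.4855 | 0.0129 |
| 8 | 2.5123 | 0.0120 |
| 9 | 2.5352 | 0.0112 |
| 10 | 2.5550 | 0.0106 |

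The stated pair is the 10-look row. At 8 looks the pair would be ±2.512 and 0.012.

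**Step 3: other readings.**

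- Eight looks with another overall two-sided level: 0.01 gives 3.078, 0.025 gives 2.770 and 0.10 gives 2.225.
- Eight interim looks plus a separate final comparison (K = 9): 2.535. Its p rounds to 0.011, but the boundary differs.
- Eight looks with Pocock-type alpha spending: not constant, falling from 2.585 to 2.448.
- Eight looks with Bonferroni or Šidák: 2.734 or 2.727.

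None gives a constant 2.555.

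**Step 4: overall error if ±2.555 is used.** The same integration gives 0.0448 for K = 8, 0.0475 for K = 9 and 0.0500 for K = 10.

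**Step 5: size in practice.** The shift is 2.555 − 2.5123 = 0.0427 in Z, and 2.555/2.5123 = 1.017, so the risk difference needed rises by 1.7%. In infants between arms this is 0.0427·√(2np(1−p)), where n is the number per arm and p an assumed event rate:

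| n per arm | p = 10% | p = 50% |
|---|---|---|
| 50 (look 1) | 0.13 | 0.21 |
| 400 (look 8) | 0.36 | 0.60 |

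At an assumed 15% rate and 400 per arm, the standard error of the difference is √(2·0.15·0.85/400) = 0.02525. The difference needed at look 8 is then 6.45 percentage points with 2.555, against 6.34 with 2.512.

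If the expected Z at look 8 is 2.5 in the direction of harm, the chance of crossing at any look falls from 0.58 to 0.56. If it is 3.0, it falls from 0.75 to 0.74. The mean look of first crossing, counting non-crossers as 8, moves by about 0.1 in both cases. These drifts are illustrative; the protocol gives none.

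**The case against.** **Nothing in the plan turns on the constant.** Crossing triggers no stated action, the Chair hears of any emerging trend well below either boundary, and the efficacy test, sample size and futility rule are untouched. This stands. It sets the priority of the correction but does not make the sentence right.

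**The two DSMC meetings could make up the ten.** Eight comparisons plus the meetings at 50% and 75% add to 10, and those meetings run on a different clock (36-week evaluation rather than death, discharge, transfer or 120 days). This may be where ±2.555 came from. But the meetings receive the same reports rather than new comparisons, and the sentence itself counts 8. Two extra looks would also not be equally spaced. If they fell 2% to 6% of the information after looks 4 and 6 (an assumption), the constant would be about 2.525 to 2.529, not 2.555.

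**The mismatch rests on an alpha that the plan does not state.** This is so. For ±2.555 to be right at 8 looks, however, the overall alpha would have to be about 0.045, a level the protocol nowhere mentions, while its efficacy sample sizes match 0.05.

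**Other loose ends matter more than 0.0448 against 0.05.** The section does not say whether the event types are pooled or tested separately. If they are tested separately, neither constant holds the error across them at 0.05. And the eighth look comes once all infants have reached status, too late to affect enrolment or treatment. Both points are fair, but they are separate from the mismatch.

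**Conclusion.** The concern holds. At an overall two-sided 0.05 with equally spaced looks, the stated 8 looks do not give ±2.555; they give ±2.512, and the stated pair belongs to 10 looks. None of the alternative readings examined reconciles the sentence. The arithmetic is certain once alpha is fixed, and the only assumption behind the mismatch is the overall 0.05.

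The error runs in the conservative direction for false alarms and so slightly against detecting harm. The loss is under two percentage points in the chance of crossing at the drifts examined, and the other reporting routes in the same section limit it further. It should be corrected because it is a stated monitoring threshold, not because it endangers the trial's conclusions.

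**What to change.** In section (8)(f)(ii), state the overall alpha and the number of looks for the serious adverse event comparison, and give the boundary that follows from them:

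- 8 looks at overall two-sided 0.05: ±2.512, nominal p 0.012.
- 9 looks, if a separate final comparison is intended: ±2.535, nominal p 0.011.
- 10 equally spaced looks, if that is what was meant: list them and keep ±2.555, nominal p 0.011.

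The cost is one sentence. With 8 looks, data collection, sample size and the number of comparisons stay as they are.
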